### 11.1.1 Safety and Tolerability Evaluations:

The following analyses will be conducted on the Safety population and the two mITT subpopulations.

Continuous safety data will be summarized with descriptive statistics (arithmetic mean, standard deviation [SD], median, minimum, and maximum) by treatment group. Categorical safety data will be summarized with frequency counts and percent of patients by treatment group. Adverse events (AEs) will be coded using the most current Medical Dictionary for Regulatory Activities (MedDRA®) available. A by-participant AE data listing, including verbatim term, preferred term, system organ class, treatment, severity, and relationship to study device will be provided. The number and percent of participants experiencing procedure and device related AEs and serious AEs will be summarized by treatment group, system organ class, and preferred term.

Laboratory evaluations and vital signs assessments will be summarized by treatment group and protocol specified collection time point. A summary of change-from-baseline at each protocol specified time-point by treatment group will also be presented. "Shift Tables" will be provided to summarize count and percent of patients with changes from baseline normal range status (below, within, above) to on/post-treatment normal range status.

Further details regarding presentation and analysis of safety data will be detailed in the statistical analysis plan (SAP).

### 11.1.2 Effectiveness evaluations:

The primary endpoint will be assessed in each modified intent-to-treat (mITT) population in step-wise fashion beginning with the primary sub-population. If a significant beneficial effect is met for CytoSorb over control at a one-sided overall 0.025 level of significance, then the study will be considered to be a primary endpoint statistical success on this subpopulation and testing will proceed to the secondary sub-population. Otherwise the study will be considered to have statistically failed the primary endpoint.

We have selected to use a modified intent-to-treat population (mITT) population to avoid the consequence of including patients that were excluded from the study after randomization due to administrative reasons.

Use of the mITT population as defined is not anticipated to result in bias or informative censoring of the data.

The primary endpoint (rank order presence and severity of AKI) will be compared between treatments with Wilcoxon Rank Sum test. Continuous endpoints will be assessed via ANCOVA with baseline value as covariate. Binary endpoints will be assessed via unconditional exact binomial test. The primary endpoint will be summarized by subgroup factors, e.g., those who receive IV contrast within 48 hours prior to surgery versus those who do not. Additionally, subgroup-by-treatment interaction may be tested via generalized ordered categorical model and/or for binary combinations of outcomes (e.g., presence / absence of any AKI, and/or severe AKI) by logistic regression. Details will be in the SAP.

### 11.2 Statistical Power and Sample Size Determination

The REFRESH II study hypothesis is that, for patients at increased risk for AKI based upon use of the Cleveland Clinic Score for stratification of the risk of cardiac surgery associated AKI (CSA-AKI), the intra-operative usage of the CytoSorb device in addition to the standard of care in a bypass circuit during cardiopulmonary bypass will decrease the overall incidence and/or proportion of acute kidney injury (AKI) by stage as defined by the Kidney Disease Improving Global Outcomes (KDIGO) clinical practice guideline definition of acute kidney injury. The AKI Stage is scored as 0, 1, 2 or 3. AKI Stage of 0 indicates no AKI, and AKI stages 1, 2 and 3 indicate mild, moderate, and severe AKI, respectively. Success will be defined by demonstrating a shift in distribution toward overall less severe AKI or fewer incidences of AKI in the CytoSorb population.

The distribution of AKI Stage (0, 1, 2, 3) expected in the control group was estimated from prior data. Sample trial outcomes for which power was computed are summarized in **Error! Reference s ource not found.** below for total N=267 patients in the primary analysis subgroup ("without HCA", randomized 1:1). The proportion of "without HCA" patients will be at least 2/3 of the total sample size 400. 420 patients will be enrolled to account for an expected 5% premature withdrawal rate. Power was computed for comparing binomial proportions of patients with AKI Stage 1, 2, or 3 (or i.e., any AKI); proportions with AKI Stage 2 or 3; and for an ordered categorical rank test comparing the distribution of AKI Stages 0, 1, 2, 3 between treatments. Since it is uncertain whether CytoSorb will lower the overall AKI rate or that of Stages 2 and 3, the ordered categorical test will be primary, i.e., the primary null and alternative hypotheses are

- H0:  $\pi 00 = \pi 01$ ,  $\pi 10 = \pi 11$ ,  $\pi 20 = \pi 21$ ,  $\pi 30 = \pi 31$
- H1:  $\{\pi 30 \ge \pi 31 \text{ and/or } (\pi 20 + \pi 30) \ge (\pi 21 + \pi 31) \text{ and/or } (\pi 10 + \pi 20 + \pi 30) \ge (\pi 11 + \pi 21 + \pi 31)\}$  AND one or more of the above is strictly ">"

where  $\pi i0$  is the proportion of control patients in AKI level i (i=0, 1, 2 and 3) and where  $\pi i1$  is the proportion of CytoSorb patients in level i. Note that level i=0 is no AKI. The test of the null

hypothesis will be carried out at an overall one-sided 0.025 level of significance using a one-sided Wilcoxon Rank Sum test, taking into account the interim analyses as described below.

### 11.2.1 Interim Analyses

Specifically, since the treatment difference could be larger or smaller than expected, interim analyses will be carried out for potential (NON-BINDING) early stopping for an efficacy or futility conclusion.

Note that the BLINDED combined AKI incidence rate will be monitored throughout the trial to inform on enrichment with patients at higher risk of AKI so as to yield sufficient AKI events to improve the expected precision of the treatment comparison.

Table 5: Overall Power for the ordinal outcome, the Any AKI dichotomous outcome (labeled Stages 1,2,3 below), and the Moderate/Severe AKI dichotomous outcome (labeled Stages 2,3 below).

		Р	ercent of	Patients	with Ind	icated AKI Sta	ge
Al	KI Stage>	0= no AKI	Stage 1	Stage 2	Stage 3	Stages 1,2,3	Stages 2,3
Example 1	CytoSorb	36%	53%	10%	1%	64%	11%
N=267	Control**	24%	47%	26%	3%	76%	29%
	power*>		0.9	0.57	0.96		
Example 2	CytoSorb	44%	40%	14%	2%	56%	16%
(total N=267)	Control**	24%	47%	26%	3%	76%	29%
	power*>		0.9	0.94	0.72		
* power to y with total N	ield statistical "without HCA	ly significa \" patients 1	nt (alpha= andomize	0.025 1-s	sided) dif	ference between	treatments

Note that the dichotomous outcomes will be considered secondary. The Table 5 power calculations do not consider the planned interim analyses. They are presented for reference, and to demonstrate the rationale for the primary analysis method based on the ordinal outcome. Note that for example 1, had the primary endpoint been the dichotomous outcome any AKI, power would have been only 57%. For example, 2, had the primary endpoint been the dichotomous outcome moderate/severe AKI, power would have been only 72%. For both examples 1 and 2, power is over 90% via the ordinal outcome.

Simulations were carried out for a Group Sequential Design (GSD) planned for Total N=267 "without HCA" patients (randomized 1:1), with Interim Analyses (IA) after AKI status (Stage 0,1,2,3) is determined for 138 (IA1 at  $\frac{1}{2}$  total N) and N=200 (IA2 at  $\frac{3}{4}$  total N). NON-BINDING early stopping for efficacy is considered if p<0.001 at IA1 or IA2; and NON-BINDING early futility stopping is considered if the Conditional Power (CP) is less than 5%. The final analysis requires p<0.0247 1-sided in order to control the overall type 1 error at 0.025 1-sided.

**NOTE**: CP is the probability of a statistically significant (alpha=0.0247 1-sided) at the final analysis (N=267) if the TRUE underlying between-treatment difference is equal to that observed at the IA. These p-value boundaries for efficacy conclusions control the overall type 1 error at 0.025 1-sided.

### 11.2.1.1 Biomarker Interim Review

A review of biomarker results will be completed at the time of the interim analysis. If insufficient data exist to enable detection of treatment effect, then the number of patients providing biomarkers may be increased. Methods used to determine the required biomarker sample size increase along with the revised number for patients will be detailed in an amendment to the protocol following the analysis.

### 11.2.2 Sample Size Re-estimation

An option to increase sample size (SSR, i.e., Sample Size Re-estimation) is also considered. SSR is based on the IA2 results using CP to estimate the sample size necessary to boost the CP to 88%, assuming the observed response proportions are the TRUE underlying proportions. CP is the probability of a significant result at final analysis assuming the observed response proportions are the TRUE underlying ones. The design works as follows at the IA:

- If CP<5%, the trial MAY be stopped for futility
- If p<0.001 1-sided, the trial MAY be stopped for an early efficacy conclusion
- If  $5\% \le CP < 50\%$  (unfavorable zone), the trial continues to the planned N=267
- If 50% ≤ CP < 88% (promising zone), sample size is increased to that required to boost CP to 88%

  - $\circ$  If that sample size exceeds N=333, the trial continues to that N=333
- If CP ≥ 88% and p>0.001 1-sided (favorable zone), the trial continues to N=267 subjects, as originally planned

This is the "promising zone" sample size re-estimation (SSR) design of Mehta & Pocock (2011), which uses the work of Chen, DeMets, Lan (2004) to justify preservation of type 1 error for the final analysis based on the combined data from the entire trial. The power and performance characteristics based on 10,000 simulations of this design are summarized in Table 6 below for 6 TRUE underlying scenarios and associated analyses based on either the binary endpoint of

proportion of patients with AKI or the corresponding ordered categorical test, each via normal approximation. [NOTE: power and design performance characteristics were computed via Cytel's EAST software, which uses normal approximation for GSD calculations and adaptive design simulations. The actual treatment group comparisons on the primary endpoint will be using the Wilcoxon Rank Sum test using the GSD stopping boundaries mentioned above; details to be specified in the SAP; treatment group comparisons on the dichotomous endpoints will be carried out using the chi-square test.] Effect Size (mean difference divided by SD) was computed for the two categorical distributions in the table above. The binary endpoint differences also correspond to those of AKI Stages 1, 2, 3 and AKI Stages 2, 3 in Table 5 above. Note that the ordered categorical test preserves the power at over 80% for both distributions, whereas the power for binary rate differences less than 0.15 is much less than 80%.

For the Scenario A in the table below, the statistical design described above was simulated 10,000 times with responses generated from TRUE underlying response rate 0.76 for control and 0.61 for CytoSorb. 92% of those simulations yielded a resultant p-value at one of the 3 analysis (IA1, IA2, or final analysis) that was lower than the boundary for that analysis (p<0.001 1-sided for IA1 and IA2, and p<0.0247 for the final analysis). If there was no efficacy conclusion at IA1 and IA2 and the IA2 result was "promising" (i.e.,  $50\% \le CP < 88\%$ ), then the sample size was increased to boost CP toward 88%, resulting in power to 97% for those IA2 outcomes. The average "without HCA" sample size across the 10K simulations was 221, and 320 for the subset of simulations that yielded a CP in the promising zone. 3% of the simulations yielded p<0.001 1-sided at IA1 and 22% at IA2; 46% of simulations yielded p<0.0247 1-sided at the final analysis. 6% of the simulations proceeded past IA2 with IA2 result in the "unfavorable" zone ( $5\% \le CP < 50\%$ ); 12% in the "promising" zone ( $50\% \le CP < 88\%$ ); and 32% in the "favorable" zone ( $CP \ge 88\%$  and IA2 p-value > 0.001 1-sided). Those proportions of outcomes represent the estimated probabilities of those outcomes for the actual trial.

Scenarios A, B, C, and D represent GSD+SSR design options based on the proportions of patients with AKI (A & B corresponding to Example 1 in Table 5) or with severe AKI (C and D corresponding to Example 2 in Table 6); Scenarios E and F (corresponding to the ordered categorical examples 1 and 2 in Table 6) represent GSD+SSR design options based on the ordinal AKI Stage 0,1,2,3 endpoint. All scenarios were assessed via normal approximation to those respective distributions as listed below in Table 6.

Scenario>	Α	В	С	D	Е	F
TRUE underlying AKI rate control	0.76	0.76	0.29	0.29		
TRUE underlying AKI rate CytoSorb	0.56	0.64	0.11	0.16		
TRUE underlying Effect Size (ordinal)					0.39	0.42
overall power (alpha=0.025 1-sided)	0.92	0.55	0.96	0.70	0.88	0.92
power if IA2 promising	0.97	0.83	0.97	0.87	0.93	0.95
average sample size	221	237	215	243	227	219
average sample size (if IA2 promising)	320	323	318	322	324	324
Probability of "futility" at IA1	0.03	0.19	0.01	0.11	0.05	0.0
Probability of "futility" at IA2	0.01	0.07	< 0.01	0.05	0.02	0.0
Probability of "futility" at Final Analysis	0.04	0.19	0.02	0.14	0.05	0.04
Probability of "efficacy" at IA1	0.25	0.05	0.28	0.08	0.21	0.2
Probability of no "efficacy" at IA1 but efficacy IA2	0.22	0.06	0.25	0.10	0.19	0.22
Probability "efficacy" at Final Analysis	0.46	0.44	0.43	0.53	0.48	0.4
Probability IA2 unfavorable	0.06	0.21	0.06	0.16	0.09	0.0
Probability IA2 promising	0.12	0.18	0.09	0.19	0.14	0.1
Probability of no "efficacy" at IA2 but IA2 favorable	0.32	0.24	0.31	0.31	0.30	0.2

Table 6: Performance Characteristics for Group Sequential Design with Sample Size Re-Estimation Option for binary and ordinal AKI endpoint

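### The ordinal effect sizes 0.39 and 0.42 in protocol Table 6 do not follow from the printed Table 5 by the stated definition, and they understate the power of the primary test

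*Protocol*

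**What the plan says.** Table 5 (protocol 11.2.1) gives the assumed percentages in AKI stages 0/1/2/3: control 24/47/26/3, CytoSorb 36/53/10/1 in Example 1 and 44/40/14/2 in Example 2. For the fixed design with 267 patients, the text under it concludes: "For both examples 1 and 2, power is over 90% via the ordinal outcome".

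Section 11.2.2 turns to the group sequential design with sample size re-estimation and explains the ordinal input to the simulations: "Effect Size (mean difference divided by SD) was computed for the two categorical distributions in the table above". It names neither the scale (stage scores or ranks) nor the SD. It adds that the software uses a normal approximation and that the real comparison will be a Wilcoxon rank sum test.

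The mapping is: "Scenarios E and F (corresponding to the ordered categorical examples 1 and 2 in Table 6) represent GSD+SSR design options". The examples are in Table 5, so I read the reference to Table 6 as a slip. Table 6 lists ordinal effect sizes 0.39 (E) and 0.42 (F) and overall power 0.88 and 0.92.

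**The concern.** E and F are the only adaptive-design operating characteristics given for the primary ordinal endpoint; A to D concern binary endpoints. If 0.39 and 0.42 are not what the stated definition yields from Table 5, a reader cannot rebuild the primary-endpoint power. The other rows for E and F (stopping probabilities, zone probabilities, average sample size) inherit the same input. Two signs suggest a mismatch. Example 1 and Example 2 have almost the same standardised mean difference on the stage scale, yet Table 6 separates them. And Example 1 is said to exceed 90% power in the fixed design, which an effect of 0.39 does not deliver at N=267.

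**Working it through.** **1. Reproduce Table 6 from its own inputs.** I simulated the stated design by normal approximation: looks at 138, 200 and 267; p<0.001 at each interim and p<0.0247 at the end; futility stop if conditional power (CP) is below 5%; promising zone 50% to 88%; cap 333. An effect of 0.39 gives power 0.883 (stated 0.88) and 0.42 gives 0.922 (stated 0.92). For E, the average N is 229 (stated 227), efficacy at the first interim 0.21 (0.21) and promising 0.14 (0.14). So the table follows from 0.39 and 0.42. Some F cells are cut off in the text available and were not checked.

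**2. Apply the stated definition to stage scores 0 to 3.**
- Control: mean 0.47 + 2×0.26 + 3×0.03 = 1.08; variance 1.78 − 1.08² = 0.6136; SD 0.783.
- CytoSorb, Example 1: mean 0.76; variance 1.02 − 0.76² = 0.4424; SD 0.665.
- CytoSorb, Example 2: mean 0.74; variance 1.14 − 0.74² = 0.5924; SD 0.770.

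| SD used | Example 1 (difference 0.32) | Example 2 (difference 0.34) |
|---|---|---|
| Pooled (0.727; 0.777) | 0.440 | 0.438 |
| Control (0.783) | 0.409 | 0.434 |
| CytoSorb (0.665; 0.770) | 0.481 | 0.442 |
| Total, arms combined | 0.430 | 0.428 |
| Stated in Table 6 | 0.39 | 0.42 |

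No choice of SD gives the stated pair from the printed percentages.

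**3. Find what does give it.** Let P be the chance that a control patient has a higher stage than a CytoSorb patient, counting ties as one half.
- Example 1: P = 0.4303 + 0.3618/2 = 0.6112; √12 × (P − 0.5) = 0.385.
- Example 2: P = 0.4546 + 0.3306/2 = 0.6199; √12 × (P − 0.5) = 0.415.

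These round to 0.39 and 0.42. This is the Wilcoxon effect for untied data. Here about 36% and 33% of between-arm pairs are tied. The tie correction divides by √(1 − Σ a³), where a is the average proportion in each stage:
- Example 1: a = 0.30, 0.50, 0.18, 0.02; 1 − Σ a³ = 0.842; effect 0.385/0.918 = 0.420.
- Example 2: a = 0.34, 0.435, 0.20, 0.025; 1 − Σ a³ = 0.870; effect 0.415/0.933 = 0.445.

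**4. Fixed-design power against Table 5.** Power = Φ(effect × √(133.5/2) − 1.96), and √66.75 = 8.17.
- Effect 0.39: Φ(3.186 − 1.960) = 0.890, which is not above 90%.
- Tie-corrected 0.420 and 0.445: 0.929 and 0.953. Direct simulation of the tie-corrected test gives 0.935 and 0.958. Both agree with Table 5.

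**5. Adaptive-design power for the test itself.** I drew multinomial data from Table 5, used the tie-corrected Wilcoxon statistic and applied the stated rules (200,000 trials per scenario):

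| | E simulated | E stated | F simulated | F stated |
|---|---|---|---|---|
| Overall power | 0.93 | 0.88 | 0.95 | 0.92 |
| Efficacy at first interim | 0.26 | 0.21 | 0.31 | cut off |
| Promising zone | 0.12 | 0.14 | 0.09 | cut off |
| Average N | 221 | 227 | 213 | 219 |

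With the protocol's 10,000 simulations, the standard error of a power of 0.88 is √(0.88×0.12/10,000) = 0.003, so a gap of 5 points is not simulation noise.

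**The case against.** The strongest reply is that the label may be literally true. Table 5 prints whole percentages and the protocol does not name the SD. I drew unrounded distributions consistent with every printed cell and both printed margins, sharing one control row. With the control SD, the effect ranges over about 0.38 to 0.44 in Example 1 and 0.40 to 0.47 in Example 2. About 3% of the draws round to 0.39 and 0.42 together. With the pooled SD, Example 1 does not go below 0.40. So rounding can just reach the pair, under one choice of SD. That stands. It means the values are not reproducible from the printed table, not that they are proven to be mislabelled.

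Second, the untied Wilcoxon effect is itself a mean rank difference over a rank SD, so the unspecified label could cover it, and it is a recognised conservative approximation. That also stands. That it is the source is my inference from the match.

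Third, the above-90% figure is for a fixed design and section 11.2.1 says Table 5 ignores the interim looks, so 0.88 in Table 6 need not equal it. That is correct. The comparison in step 4 avoids this by putting 0.39 into the fixed design, where it gives 0.89. The tension there is only about one point.

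A reader might infer that the Table 6 power is miscalculated, or that the trial was underpowered. The documents do not support either. Table 6 is openly a normal approximation and reproduces from its displayed inputs, and the departure understates power.

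**Conclusion.** The point holds in a limited form. The effect sizes 0.39 and 0.42 are not reproduced by the stated definition from the printed Table 5. As inputs they understate the Wilcoxon test by about 5 points of power in E (0.93 against 0.88) and 3 in F (0.95 against 0.92). Tables 5 and 6 appear to rest on different effect measures for the same distributions.

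This assumes that the Wilcoxon test uses the tie-corrected variance, since the protocol is silent on ties; that the printed percentages are taken as exact; and that futility stops are applied as in Table 6.

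The discrepancy is conservative. N=267, the cap of 333, the boundaries and the statement that ordinal power exceeds 80% in both examples all stand. The practical weight is low. SAP section 4.1 says the study stopped before any interim analysis, with 151 enrolled, and SAP section 6.7.1.1 uses Fisher's exact tests. What remains is the accuracy of the design record, to which SAP section 5 still refers for the sample size.

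**What to change.** In section 11.2.2, state the scale of the effect size, the SD used and how ties are handled. Then do one of two things:
- rerun E and F with the tie-corrected Wilcoxon effects (about 0.42 and 0.45) and restate all their rows; or
- keep 0.39 and 0.42, if that is how they were obtained, and label them an untied Wilcoxon approximation that is conservative for this endpoint.

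In either case, add a sentence reconciling the effect measure with the fixed-design power in Table 5, and correct the reference that places Examples 1 and 2 in Table 6. The cost is at most one software rerun and a table correction. With the trial stopped, a note to the design record would be enough.

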### 11.3 Study Success

An individual study subject will be defined as a success if during the 48 hours following surgery, they do not receive a diagnosis of AKI by the KDIGO Guidelines. In contrast, a patient whose clinical parameters result in a diagnosis of AKI will be classified according to AKI stage. Study success will be defined by demonstration of a statistically significant shift in distribution of AKI Stages 0, 1, 2, 3 toward less severe and/or no AKI with CytoSorb in comparison to standard of care.

### 11.4 Treatment of Missing or Spurious Data

Multiple imputation methodology will be used for missing data imputation; details will be in the SAP.

### **11.5 Disposition and Baseline Characteristics**

Number and percent of patients discontinuing prematurely from the study will be provided by treatment group and by reason discontinued. All data for background and demographic variables will be listed by treatment group and subject. Summary statistics will be provided by treatment group. Relevant medical history, current medical conditions, results of laboratory screens, and any

other relevant information will be summarized by treatment group and listed by treatment group and subject

## **12. DATA HANDLING AND RECORD KEEPING**

Each participating site will maintain appropriate medical and research records for this trial, in compliance with ICH E6 Section 4.9 and regulatory and institutional requirements for the protection of confidentiality of subjects. As part of participating in a manufacturer-sponsored study, each site will permit authorized representatives of the sponsor(s), the sponsor's designee, and regulatory agencies to examine (and when required by applicable law, to copy) clinical records for the purposes of quality assurance reviews, audits, and evaluation of the study safety and progress.

Source data are all information, original records of clinical findings, observations, or other activities in a study necessary for the reconstruction and evaluation of the trial.

The Investigator is responsible for ensuring the accuracy, completeness, legibility, and timeliness of the data reported. All source documents should be completed in a neat, legible manner to ensure accurate interpretation of data.

